### 7.6.2 Increase in dose of existing diuretic or addition of new diuretic due to fluid retention

A ‘diuretic due to fluid retention’ is any medication on the **Previous/Concomitant Medications** eCRF as defined in Appendix 14.4 with the indication ‘Adverse Event’ where the ‘Main Event’ is fluid retention as defined in Appendix 14.3. The existing diuretic is 25 mg hydrochlorothiazide as part of the standardized background antihypertensive therapy.

This endpoint will be analyzed similarly to MACE-plus.

### 7.6.3 Analysis of biomarker variables

Ratios to baseline of NT-proBNP will be log transformed (base e). Observed values at Baseline, visits in DB and SB part, and changes from baseline (including the geometric mean [and SD] ratio of post-baseline to baseline) will be summarized using descriptive statistics. Ratios to DB-WD baseline of NT-proBNP in the DB-WD part and up to EOS will be analyzed similarly, but with baseline replaced by DB-WD baseline.

Ratios to baseline of Mid-regional pro-atrial natriuretic peptide and Troponin will be analyzed similarly to NT-proBNP.

The analysis of biomarkers characterizing the endothelin system and renin angiotensin system activity will be addressed in a separate SAP.

## 7.7 Overview of safety analyses

The safety analyses are summarized here:

**Table 5 Summary of safety analyses**

Endpoint	Part	Analysis set	Visits	Statistical analysis (if applicable)
Adverse events	DB	SAF	NA	
	SB	rSAF	NA	
	DB-WD	mSAF	NA	
Serious adverse events	DB	SAF	NA	
	SB	rSAF	NA	
	DB-WD	mSAF	NA	
Adverse events leading to treatment discontinuation	DB	SAF	NA	
	SB	rSAF	NA	
	DB-WD	mSAF	NA	
Adverse event of special interest	DB	SAF	NA	
	SB	rSAF	NA	
	DB-WD	mSAF	NA	
Laboratory values and changes from baseline	DB+SB	SAF	Week 4, 6, 12, 20, 28 and 36	
Laboratory values and changes from DB-WD baseline (Week 36)	DB-WD	mSAF	Week 40, 44 and 48	
Number (%) of subjects with marked abnormalities laboratory values	DB,	SAF	NA	
	SB	rSAF		
	DB-WD	mSAF	NA	
Vital signs values and changes from baseline over time	DB+SB	SAF	Week 2 up to Week 36	
Vital signs values and changes from DB-WD baseline (Week 36) over time	DB-WD	mSAF	Week 38 up to Week 48	
ECG values over time and changes from baseline over time	DB+SB	SAF	Week 2 up to Week 36	

Endpoint	Part	Analysis set	Visits	Statistical analysis (if applicable)
ECG values over time and changes from DB-WD baseline (Week 36) over time	DB-WD	mSAF	Week 48	
Number (%) of subjects with marked abnormalities ECG values	DB	SAF	NA	
	SB	rSAF		
	DB-WD	mSAF	NA	
MACE-plus	DB+SB	SAF	NA	Cox model
	DB-WD	mSAF	NA	Cox model
MACE-plus	All	SAF	NA	Incidence rate
Increase or addition of diuretic	DB+SB	SAF	NA	Cox model
	DB-WD	mSAF	NA	Cox model

DB = double-blind; DB-WD = double-blind withdrawal; ECG = electrocardiogram; MACE = major adverse cardiac event; mSAF = modified Safety analysis set; NA = Not applicable as not by visit; NT-proBNP = N-Terminal pro-brain natriuretic peptide; rSAF = restricted Safety analysis set; SAF = Safety analysis set; SB = single-blind.

## **8 GENERAL STATISTICAL METHODOLOGY**

### **8.1 General rules for data presentations**

When data are summarized by study part and treatment group one of the following presentations will be used.

For the DB part:

Aprocitentan 12.5 mg N = xxx	Aprocitentan 25 mg N = xxx	Placebo N = xxx
---	---	----------------------------------

For the SB aprocitentan part:

Aprocitentan 25 mg N = xxx
---

For the combined DB+SB part:

	Aprocitentan 12.5 mg N = xxx	Aprocitentan 25 mg N = xxx	Placebo N = xxx
DB part	xx	xx	xx
SB part	xx	xx	xx
By randomized treatment group			
SB part		xx	
Combined treatment group			

For the DB-WD part:

Aprocitentan 25 mg N = xxx	Placebo N = xxx
---------------------------------------	----------------------------

Here N indicates the number of subjects in a treatment group in the analysis set.

Listings for other than safety variables will be sorted by randomized treatment (A = aprocitentan 12.5 mg, B = aprocitentan 25 mg, C = placebo), re-randomized treatment (D = aprocitentan 25 mg, E = placebo), country, subject number (ascending) and, when appropriate, by visit / date of assessment (ascending). Subjects who are not re-randomized will be listed after those who are re-randomized. Run-in failures (i.e., subjects in run-in who were not randomized) will be listed next and labeled 'RI failure' and screening failures (i.e., screened subjects who did not enter the run-in) will be listed last and labeled 'SCR failure'.

In listings for safety variables, randomized and re-randomized treatment will be replaced by actual treatment in the DB and DB-WD parts, respectively.

Unless noted otherwise, the following descriptive statistics will be used:

- Number (%) of subjects for categorical variables (missing will not be included in the calculation of %).
- Number of non-missing values, mean, SD, median, Q1, Q3, minimum, maximum for continuous variables.
- The category missing will be displayed only if there are missing values.

## 8.2 Analysis details

### 8.2.1 Mixed model for repeated measurements

This model is used, for example, for the main analyses of the primary and the key secondary endpoints.

Assuming the data are in ‘long’ format (i.e., one row for each subject/visit) example SAS® statements for the primary endpoint analysis are:

```
proc mixed data=db;
  class subjid trt01pn avisitn;
  model chg=trt01pn avisitn trt01pn*avisitn base base*avisitn/ ddfm=kr;
  repeated avisitn/ subject=subjid type=un;
  lsmeans trt01pn*avisitn/ diff=control ('3' '6') alpha=0.025;
run;
```

The data set *db* includes baseline SiSBP (*base*) as well as changes (*chg*) from baseline to Weeks 2 and 4. Furthermore, *trt01pn* equals 1, 2 and 3 for aprocitentan 12.5 mg, aprocitentan 25 mg and placebo in the DB part, respectively, and *avisitn* is 5 and 6 for Weeks 2 and 4, respectively. The Bonferroni correction [Section 6.1] will be applied by comparing the two-sided p-values vs 0.025 (rather than adding *adjust=bonf* to the *lsmeans* statement).

Again, assuming the data are in ‘long’ format example SAS® statements for the secondary endpoint analysis are:

```
proc mixed data=dbwd;
  class trt01pn subjid trt03pn avisitn;
  model chg=trt01pn trt03pn avisitn trt03pn*avisitn wk36 wk36*avisitn/
  ddfm=kr;
  repeated avisitn/ subject=subjid type=un;
  lsmeans trt03pn*avisitn/ diff=control ('5' '13') alpha =0.05(1);
run;
```

The data set *dbwd* includes DB-WD baseline (Week 36) SiSBP (*wk36*) as well as changes (*chg*) from DB-WD baseline (Week 36) to Weeks 38 and 40. Furthermore, *trt03pn* equals 4 and 5 for aprocitentan 25 mg and placebo in the DB-WD part, respectively, and *avisitn* is 12 and 13 for Weeks 38 and 40, respectively. Note that *trt01pn* (treatment in the DB part) is now used as a stratum.

 The alpha level needs to be adjusted to 0.025 in case one of H10 and H20 has been rejected.

## 8.2.2 Controlled imputation assuming missing not at random

Sensitivity analyses assuming the data are MNAR in the aprocitentan groups (and MAR in the placebo group) will be performed using MI. These will be performed assuming a monotone missing data pattern (i.e., if data are missing at a given visit, they are also missing at subsequent visits). Any non-monotone missing data will first be imputed under MAR, which is considered reasonable because the proportion of non-monotone missing data (i.e., AOBPM missing at Week 2, but observed at Week 4) is expected to be low.

Assuming the data are in 'wide' format (i.e., one row for each subject and a variable for each visit) example SAS® statements for the primary endpoint are:

```
proc mi data=db nimpute=250 seed=63496 out=mono;  
  var base chg2 chg4;  
  mcmc impute=monotone;  
run;
```

Here *chg2* and *chg4* are the changes from baseline to Weeks 2 and 4 in SiSBP, respectively. Note that treatment is not included in the imputation model.

Two control-based MI analyses will be performed under MNAR, a CR and a J2R approach [Carpenter 2013]. In these approaches, MI of missing values will be performed based on the assumption that subjects with missing data in the aprocitentan arms follow the trajectory of the placebo arm, conditional on subjects' data available prior to discontinuation (baseline as well as available post-baseline SiSBP for the CR approach; baseline SiSBP only for the J2R approach). Imputation is performed sequentially, one visit at a time [Ratitch 2013]. At each visit a regression model is fitted using data from the placebo arm only, so missing data in the aprocitentan arms are imputed based on the predicted outcome in the placebo arm.

The SAS® statements for the CR approach are:

```
proc mi data=mono nimpute=1 seed=133055 out=CR1;  
  by _Imputation_;  
  class trt01pn;  
  var base chg2;  
  monotone regression;  
  mnar model (chg2/ modelobs=(trt01pn='3'));  
run;
```

```
proc mi data=CR1 nimpute=1 seed=130871 out=CR2;  
  by _Imputation_;  
  class trt01pn;  
  var base chg2 chg4;
```

```
monotone regression;  
mnar model (chg4/ modelobs=(trt01pn='3'));  
run;
```

The variable `_Imputation_` is created by the PROC MI statement that generated the monotone missing data. Note that the second PROC MI statement for the CR approach includes change from baseline to Week 2 as a predictor for change from baseline to Week 4, meaning that subjects from the aprocitentan groups who discontinue DB treatment between Week 2 and Week 4 are regarded as subjects from the placebo group with a similar change from baseline to Week 2 in SiSBP.

The SAS® statements for the J2R approach are:

```
proc mi data=mono nimpute=1 seed=130340 out=J2R1;  
  by _Imputation_;  
  class trt01pn;  
  var base chg2;  
  monotone regression;  
  mnar model (chg2/ modelobs=(trt01pn='3'));  
run;
```

```
proc mi data=J2R1 nimpute=1 seed=125892 out=J2R2;  
  by _Imputation_;  
  class trt01pn;  
  var base chg4;  
  monotone regression;  
  mnar model (chg4/ modelobs=(trt01pn='3'));  
run;
```

Note that the second PROC MI statement for the J2R approach does *not* include change from baseline to Week 2 as a predictor for change from baseline to Week 4, meaning that subjects from the aprocitentan groups who discontinue DB treatment between Week 2 and Week 4 are 'immediately' regarded as subjects from the placebo group.

The resulting multiple data sets are subsequently analyzed using the same mixed model as for the main analysis. For this purpose, the data set from PROC MI (CR2 or J2R2 in the example), should be transposed to a 'long' format.

Results from these analyses are combined using Rubin's methodology [[Rubin 1987](#)] implemented in SAS® PROC MIANALYZE:

```
proc mianalyze parms=diffs;  
  class trt01pn avisitn;  
  modeleffects trt01pn* avisitn;
```

run;

The control-based MI models described above are pattern-mixture models, where the patterns are defined based on the subject's last visit. If the number of subjects with missing Week 4 data is greater than expected (i.e., > 5% of the FAS), the reason for premature discontinuation (lack of efficacy, AE, other) may also be considered in defining the patterns.

The SAS® statements for the key secondary endpoint are similar, only with DB-WD baseline (Week 36), Week 38 and Week 40 instead of baseline, Week 2 and Week 4, respectively.

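### The second J2R imputation step ignores the observed Week 2 (Week 38) blood pressure of placebo subjects, which contradicts the stated MAR assumption for placebo

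*SAP*

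**What the plan says.** SAP section 8.2.2 states the assumption for the control-based analyses: "Sensitivity analyses assuming the data are MNAR in the aprocitentan groups (and MAR in the placebo group) will be performed using MI". It describes the conditioning set for subjects in the aprocitentan arms as baseline plus available post-baseline values for CR, and "baseline SiSBP only for the J2R approach".

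The code for the Week 4 step differs between the two approaches:

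- **CR:** the variable list is "var base chg2 chg4", so Week 2 is a predictor.
- **J2R:** the list holds only baseline and the Week 4 change. The model statement begins "mnar model (chg4/ modelobs=(trt01pn='3", which restricts the fit to placebo records.

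The SAP says openly that the second J2R step does not "include change from baseline to Week 2 as a predictor for change from baseline to Week 4". It explains the consequence for the active arms only: "meaning that subjects from the aprocitentan groups who discontinue DB treatment between Week 2 and Week 4 are 'immediately' regarded as subjects from the placebo" arm. Nothing is said about placebo subjects. For the DB-WD part, "The SAS ® statements for the key secondary endpoint are similar", with Weeks 36, 38 and 40 in place of baseline, Week 2 and Week 4.

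Expected missingness is 5% at Week 4 (section 6.2.2) and 10% at Week 40 (section 6.3.2).

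**The concern.** The MODELOBS option decides which records fit the regression. It does not decide which missing values are filled in. No other statement limits the imputation to the aprocitentan arms, so a placebo subject with an observed Week 2 value and a missing Week 4 value is drawn from the baseline-only fit. MAR given the observed data would use the Week 2 value. The code instead assumes that placebo drop-out does not depend on Week 2 once baseline is known, which is stricter than what the text claims.

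That stricter assumption may well fail. The SAP lists lack of efficacy as a reason for stopping treatment (section 5.1.3), compares it between arms (section 6.5) and may use it to define imputation patterns (section 8.2.2).

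The main mixed model does use Week 2 for placebo. A difference between J2R and the main result would therefore mix the intended aprocitentan penalty with an undeclared change to the placebo arm.

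**Working it through.** **Inputs.** The plan gives no figure for the J2R analysis, and the documents give no SD and no correlation between visits, so there is nothing of the plan's own to reproduce. Assumed here: residual SD of change 12 mmHg, correlation between the two visits rho = 0.6, and log-odds of drop-out rising by 0.05 or 0.10 per mmHg of the earlier value. Those slopes are odds ratios of exp(0.5) = 1.65 and exp(1.0) = 2.72 per 10 mmHg, or b = 0.6 and 1.2 per SD. Losses fall after Week 2 (38) unless stated. Negative contrasts favour the drug.

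**Step 1, placebo mean.** Missing placebo values are filled with the completers' mean given baseline. To first order the completers' Week 2 values sit b x p SDs below the full arm, where p is the proportion missing, so

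bias = -p x b x rho x SD.

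- b = 0.6, p = 8%: -0.08 x 0.6 x 0.6 x 12 = -0.35 mmHg
- b = 0.6, p = 15%: -0.15 x 0.6 x 0.6 x 12 = -0.65
- b = 1.2, p = 8%: -0.08 x 1.2 x 0.6 x 12 = -0.69
- b = 1.2, p = 15%: -0.15 x 1.2 x 0.6 x 12 = -1.30

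The formula overstates at strong selection. Simulation (60 replicates of 4000 per arm, mean imputation followed by ANCOVA) gives about -1.1 for the last case, and about -0.3 to -1.1 overall.

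**Step 2, placebo defect alone.** If placebo loses its higher-pressure subjects and aprocitentan drop-out is random, simulation at 10% missing gives a null contrast of about +0.41 mmHg, against the drug. The error favours the drug only if placebo loses its lower-pressure subjects.

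**Step 3, both arms as coded, no true effect.** Aprocitentan completers are shifted by -b x p_a x rho x SD, and missing aprocitentan values take the placebo completers' mean. Subtracting the placebo bias leaves

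contrast = -b x rho x SD x (1 - p_a) x (p_a - p_p).

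With p_p = 8%, p_a = 15% and b = 0.6: -0.6 x 7.2 x 0.85 x 0.07 = -0.26 mmHg. Simulation gives -0.18 to -0.26 at this slope and -0.38 to -0.44 at the steeper one. The expression is zero when p_a = p_p with the same mechanism, and when b = 0.

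**Step 4, a true effect.** With a true effect of -5.5 and 15% placebo / 8% aprocitentan missing, the intended J2R contrast is -5.5 x (1 - 0.08) = -5.06. As coded, simulation gives about -4.6 to -4.8, which understates the effect.

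**Step 5, trial-sized check under other assumptions.** No true effect, SD 15, rho 0.7, odds of drop-out doubling per SD, 1200 replicates with 8 imputations. The nominal one-sided rate is 1.25% for the DB part (two-sided 0.025) and 2.5% for DB-WD (two-sided 0.05).

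| Part, subjects per arm, missing | Who drops out | Contrast, mmHg | One-sided false positives for drug |
|---|---|---|---|
| DB, 243, 5% | drug high, placebo random | -0.27 | 2.4% |
| DB, 243, 5% | placebo high, drug random | +0.33 | 0.3% |
| DB-WD, 190, 10% | drug high, placebo random | -0.67 | 4.3% |
| DB-WD, 190, 10% | placebo high, drug random | +0.69 | 0.3% |
| DB-WD, 190, 10% | placebo low, drug random | -0.71 | 5.2% |
| DB-WD, 190, 10% | high in both arms alike | -0.05 | 1.8% |

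Over SD 10-20 and rho 0.5-0.8 with the same odds ratio, the Step 1 formula gives a one-arm shift of 0.17-0.55 mmHg at 5% missing and 0.35-1.11 mmHg at 10%.

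**Step 6, candidate remedies.**

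- *Week 2 residual in every arm:* null contrast within simulation error of zero (-0.08 to +0.07), and no bias in the placebo mean.
- *Week 2 restored for placebo only:* about -0.35 mmHg towards the drug under the null at equal 10% missing (SD 12, rho 0.6), and -0.75 under the Step 5 assumptions.
- *Own-arm residual for everyone:* this fails for aprocitentan subjects whose Week 2 value was itself drawn from placebo in the first J2R step. With a true effect of -5.5 and equal 10% missing, the contrast is -4.82 or -4.68 (half or all lost early) instead of about -4.98. Taking the residual from the placebo mean for those subjects restores -4.97 / -4.98.

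**The case against.** Baseline-only conditioning in the aprocitentan arms is declared in the text and explained beside the code. It is the SAP's chosen form of J2R, and a sensitivity analysis may depart from MAR on purpose. That stands: the contradiction between text and code concerns placebo only.

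A reader might infer that the coding error as such makes J2R lean towards the drug. The documents do not support that. The drug-favouring null result in Step 3 comes from the disclosed aprocitentan choice combined with unequal losses. When high-pressure subjects leave, the placebo defect pulls the other way.

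A reader might also take J2R for the main stress test of the hypotheses. Section 6.2.4 and Table 4 list it beside CR, the tipping point analysis and a hypothetical-estimand mixed model, without ranking them. No hypothesis in section 6.1 is tested on it. The main model, CR and the tipping point analysis all use Week 2.

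Finally, the size is modest. At 5% missing with moderate selection in one arm it is a few tenths of a mmHg, less if some subjects leave before Week 2, and no changed conclusion has been shown. This limits the importance of the point but does not remove the mismatch.

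**Conclusion.** The point holds for the placebo arm: the second J2R step does not deliver the MAR imputation that section 8.2.2 states, for either the primary or the key secondary endpoint. Where drop-out depends on the earlier pressure, the placebo mean is off by about -0.3 to -1.1 mmHg at 8-15% missing. Together with the disclosed aprocitentan choice, the J2R contrast can move either way: about -0.2 to -0.4 mmHg under the null at 8%/15% missing, and an understated effect when placebo loses more.

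These sizes rest on the assumed SD, correlation and drop-out mechanism, and on losses falling after Week 2 (38). The contrast is unbiased if drop-out is the same in both arms or unrelated to the earlier value. The primary and key secondary tests are not affected. The change should be made, but the trial's conclusions do not hang on it.

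**What to change.** In the second J2R step, use `var base res2 chg4` with the fit still restricted to placebo. Define `res2` within each imputation as the Week 2 change minus its predicted mean given baseline:

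- where Week 2 was observed, use the subject's own-arm mean, estimated from observed Week 2 changes;
- where Week 2 was imputed in the first J2R step, use the placebo mean.

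Placebo is then imputed under MAR as stated. Aprocitentan subjects still jump to the placebo mean but keep their own deviation. Do not restore Week 2 for placebo alone, for the reason shown in Step 6.

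Make the same change for Weeks 38 and 40, and amend the phrase "baseline SiSBP only for the J2R approach" to match. The cost is a few extra lines of code per endpoint and one text edit; no new data are needed.

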### 8.2.3 Tipping point analysis assuming missing not at random

The tipping point analysis will be performed using MI assuming a monotone missing data pattern. Any non-monotone missing data will first be imputed under MAR, as described in Section 8.2.2. Missing data will initially be imputed under MAR, but the aprocitentan groups will be 'penalized' by adding a shift of  $s$  mmHg to each imputed value. This will be done for a series of  $s$  values (henceforth, shift parameters). Only positive shift parameters will be considered since these correspond to a smaller reduction or larger increase in BP. For each shift parameter the multiple data sets are analyzed using an ANCOVA for the last time point (for the primary endpoint this is *chg4*, the change from baseline to Week 4 in SiSBP) and the results are combined using PROC MIANALYZE. This is implemented in the following SAS® macro:

```
%macro tipping (dset=, smin=, smax=, step=, seed=, out=);  
* data set &dset should be in wide format;  
  
* obtain monotone missing data pattern;  
proc mi data=&dset nimpute=250 seed=&seed out=mono;  
  var base chg2 chg4;  
  mcmc impute=monotone;  
run;  
  
proc sort;  
  by _Imputation_;  
run;  
  
data &out;  
  set _null_;  
run;  
  
ods select none;  
%do s=smin %to &smax %by &step;  
proc mi data=mono nimpute=1 seed=&seed out=tip;
```

```
by _Imputation_;
class trt01pn;
var trt01pn base chg2 chg4;
monotone regression;
mnar adjust(chg4/ shift=&s adjustobs=(trt01pn='1'));
mnar adjust(chg4/ shift=&s adjustobs=(trt01pn='2'));
run;

ods output diffs=diffs;
proc mixed data=tip;
  by _Imputation_;
  class trt01pn;
  model chg4=trt01pn base;
  lsmeans trt01pn/ diff=control('3');
run;
ods output close;

ods output parameterestimates=parmest;
proc mianalyze parms=diffs;
  class trt01pn;
  modeleffects trt01pn;
run;
ods output close;

data parmest;
  shift=&s;
  set parmest;
run;

data &out;
  set &out parmest;
run;
%end;
ods select all;
%mend tippoint;
```

An example of the associated macro call is:

```
%tippoint (dset=mono, smin=0, smax=50, step=1, seed=125160, out=tipout);
```

The p-value in data set *tipout* can be plotted vs the shift parameter. The shift parameter at which statistical significance is lost (in the DB part when the two-sided  $P > 0.025$ ) indicates

how severe departures from the MAR assumption must be to overturn the conclusions of the main analysis.

The tipping point analyses for the DB-WD part are similar to those for the DB part, except that baseline, Week 2 and Week 4 are replaced by DB-WD baseline (Week 36), Week 38 and Week 40, respectively, and the shift applies to the aprocitentan 25 mg group only.

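### The example tipping-point call in SAP 8.2.3 names the 250-fold imputed data set; if it is kept once the visible code errors are repaired, standard errors would be about 15.8 times too small

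*SAP*

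**What the plan says.** SAP 8.2.2 starts from wide data, described as "one row for each subject and a variable for each visit", and obtains a monotone missing pattern with "proc mi data=db nimpute=250 seed=63496 out=mono". After that step `mono` holds 250 copies of the trial, indexed by `_Imputation_`. The copy-reference (CR) and jump-to-reference (J2R) steps that follow read it by `_Imputation_` with one imputation each.

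SAP 8.2.3 describes one monotone step under MAR, then imputation under MAR with a shift added in the aprocitentan arms, an ANCOVA at the last time point, and pooling. The macro opens with "macro tipping (dset=, smin=, smax=, step=, seed=, out" and carries the comment "data set &dset should be in wide format". Its first step is "proc mi data=&dset nimpute=250 seed=&seed out=mono", with no BY statement.

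The call is introduced by "An example of the associated macro call is" and passes "dset=mono, smin=0, smax=50, step=1, seed=125160, out=tipout". The macro is closed and called as `tippoint`, not `tipping`, and the loop is written "do s=smin %to &smax %by &step;", without an ampersand before `smin`.

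**The concern.** The only `mono` defined before the call is the 250-fold file of 8.2.2. Passing it to a macro that imputes without BY means that the 250 rows belonging to one subject enter each analysis as 250 different subjects.

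The two syntax errors stop the program, so a programmer must repair them. Neither repair touches the `dset` argument. What remains is a valid data set with the expected variable names, and nothing in the code rejects it.

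The SAP uses the tipping point to show how badly MAR must fail before the main conclusion is overturned. An error that shrinks the standard error makes that conclusion look more robust than it is, so it runs in the sponsor's favour.

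**Working it through.** The SAP states no standard error or tipping-point result, so there is no plan figure to reproduce.

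**Inputs from the SAP.** 730 randomized (2.1), 1:1:1, so about 243 per arm; two-sided α = 0.025 per dose (6.1), z = 2.241; 5% expected missing at Week 4 (6.2.2); 250 imputations (8.2.2, 8.2.3); shifts 0 to 50 in steps of 1 (8.2.3).

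**Assumptions, not in the documents.** Effect 3.5 to 5 mmHg, SD 12 to 14 mmHg, and 10% missing as the upper case for the double-blind part.

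**Row count and standard error.** 250 × 730 = 182,500 rows per ANCOVA instead of 730. The SE falls by √250 = 15.81.

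**Tipping shift.** With effect size d, missing fraction f in the active arm and shift s, significance is lost when d − f·s = z·SE, so s = (d − z·SE)/f, with SE = SD·√(2/243). For stacked input, SE is divided by 15.81.

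- Example with d = 4, SD 14, f = 0.05: SE = 14 × 0.0907 = 1.27 and z·SE = 2.85.
  - Correct input: (4 − 2.85)/0.05 ≈ 23 mmHg.
  - Stacked input: z·SE = 2.85/15.81 = 0.18, so (4 − 0.18)/0.05 ≈ 76 mmHg.
- Least favourable corner (d = 3.5, SD 14, f = 0.10): (3.5 − 2.85)/0.10 ≈ 7 correctly; (3.5 − 0.18)/0.10 ≈ 33 stacked.
- Most favourable corner (d = 5, SD 12, f = 0.05; z·SE = 2.44): (5 − 2.44)/0.05 ≈ 51 correctly; (5 − 0.15)/0.05 ≈ 97 stacked.

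The ranges are therefore 7 to 51 mmHg correctly and 33 to 97 mmHg stacked. At 10% missing the largest stacked value is (5 − 0.15)/0.10 ≈ 48, inside the 0 to 50 grid. At 5% missing the smallest is (3.5 − 0.18)/0.05 ≈ 66, outside it.

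**Simulation of the macro's steps.** This used 730 subjects, 2% non-monotone missing data, correlation 0.6 between visits and a 5 mmHg grid of shifts. The correct runs pooled 250 imputations and the stacked runs 20. Stacked input was simulated both with the incoming `_Imputation_` overwritten and with it kept.

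| Assumed effect, SD, missing | Realised estimate | SE at shift 0, correct | SE at shift 0, stacked | Ratio | First shift lost, correct |
|---|---|---|---|---|---|
| 4, 12, 5% | −4.50 | 1.13 | 0.07 | 15.7–15.8 | 35 |
| 4, 15, 5% | −4.62 | 1.41 | 0.09 | 15.7–15.8 | 30 |
| 4, 20, 5% | −4.83 | 1.88 | 0.12 | 15.7–15.8 | 15 |
| 5, 15, 10% | −4.87 | 1.44 | 0.09 | 15.7–15.9 | 20 |

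With stacked input, significance was not lost by 50 mmHg in any of the four runs. Rubin pooling does not rescue the SE, because the between-imputation variance shrinks as well.

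The simulated shifts belong to the realised estimates, which differ from the assumed effects, so they support the SE ratio better than any particular mmHg value. The formula holds SE constant over shifts. In the simulation it rises (1.41 to 1.64 from shift 0 to 50 at SD 15), so the correct tipping shift would be somewhat smaller than the formula gives.

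**The case against.** The strongest reply is that the specified method is right. The prose describes one monotone step, the macro comment asks for wide data, and wide is defined as one row per subject, which already excludes stacked input. The call is labelled an example and the printed code cannot run. Data set names in section 8.2 are loose in any case: `db` is long in 8.2.1 and wide in 8.2.2. The author may also have meant `mono` as the already monotone file, leaving the macro's first step redundant.

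Most of this stands. It makes the consequence conditional and confines the defect to code, not method. It does not remove the defect: the call and the macro's first step cannot both be used as printed, and the repairs that the log would force leave the wrong argument in place.

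Detection is also likely. The shift-0 SE would be about one sixteenth of that in the main analysis, and each of the 51 shifts would process 250 × 182,500 ≈ 45.6 million rows. But 8.2.3 asks for no such comparison.

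A reader might infer that the analysis was in fact run on stacked data, or that it would necessarily report no tipping point. The documents support neither. They do not show how the code was executed, and whether the stacked value exceeds 50 mmHg depends on the assumed inputs. The correct value can itself reach about 51 mmHg.

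**Conclusion.** The point holds in conditional form. If the macro name and the ampersand are repaired, `dset=mono` is kept and 8.2.2 has been run first, the SE in the tipping-point analysis would be about 15.8 times too small and the tipping shift overstated. The factor follows from the 250 imputations alone. The mmHg figures rest on assumed effect, SD and missing fraction and are illustrations only.

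The reach is limited to the tipping-point analysis of the primary endpoint, and to its double-blind withdrawal counterpart if the same code is adapted; no call for that part is printed. It would be wrong to infer that the confirmatory results are in doubt. The main mixed models use no imputed data, and CR and J2R process `mono` by `_Imputation_`. The correction should be made before programming, because the remaining error flatters robustness and the code itself would not flag it.

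**What to change.** In SAP 8.2.3:

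- Call the macro with the unimputed wide data set of 8.2.2, one row per subject, under a name distinct from the long `db` of 8.2.1.
- Rename the macro's internal output so that it differs from the `mono` of 8.2.2.
- Use one macro name in the definition, the closing statement and the call.
- Write `%do s=&smin`.
- Add a check that the SE at shift 0 agrees with that of a MAR multiple-imputation ANCOVA.
- Carry the same corrections into the double-blind withdrawal version.

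The cost is a correction to the SAP code. The method, the data and the trial's conduct do not change.
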